**Visit 8 (4 to 21 days after visit 6), 9 (11 to 13 weeks after visit 2), 10 (23 to 25 weeks after visit 2)**

- I. SCID for visits 9 and 10 only
- II. Vital Signs for visit 8 only
- III. Bloods (see Appendix B and section 7.9.2 for details of the tests that will be used),
- IV. Urine Drug Screen (See Appendix B and section 7.9.2 for details of the tests that will be used.)
- V. Breathalyser
- VI. SCRAM-X removal (visit 8 only)
- VII. Relapse Prevention Based Cognitive Behavioural Therapy for visit 8 only
- VIII. Adverse Events Review
- IX. Concomitant medication review
- X. Alcohol and Drug use History
- XI. BDI
- XII. HAM-D
- XIII. POMS
- XIV. STAI
- XV. ACQ-NOW
- XVI. BPRS
- XVII. PSI

- XVIII. Alcohol Timeline Follow Back
- XIX. Drink diary
- XX. Fagerstrom Nicotine Dependence
- XXI. Craving VAS
- XXII. SF-12
- XXIII. Prose Recall
- XXIV. Delay Discounting (monetary choice questionnaire)
- XXV. Stop Signal Reaction time
- XXVI. Working Memory (digit span WAIS-IV)
- XXVII. Adverse Effects VAS
- XXVIII. Pattern Recognition Test

## 7.8 Table of study assessments

Appendix B has a table listing all the study assessment per visit..

## 7.9 Methods

### 7.9.1 *Non laboratory procedures*

Medical History: The medical history will be taken by the researcher from the patient and by referring to medical notes to measure eligibility.

The assessment days at which questionnaire and neurocognitive measures will be administered can be found in section 7. Below is a list of questionnaire and neurocognitive measures and their state of validation:

Validated Interviews and Questionnaires:

- The Structured Clinical Interview for DSM-IV/DSM-5 Disorders (SCID) is used to confirm a diagnosis of alcohol dependence and the absence of current psychiatric diagnoses which are listed as exclusion criteria (e.g. schizophrenia). This diagnostic schedule is widely used. It lasts 20-30 minutes.
- The Beck Depression inventory (BDI) is a 21 item self-rated questionnaire which will be given at varying time points to measure depressive symptoms.
- The Hamilton Depression Inventory (HAM-D) is a 21 item clinician rated depression scale.
- The Columbia Suicide Severity Rating Scale is a 6 item interview used to assess suicidal ideation and behaviour and will be used to verify the exclusion criteria of subjects with suicide ideation.

- The State form of the Spielberger Trait Anxiety inventory (STAI) questionnaire (20 items) will be used to measure anxiety throughout the study.
- The Profile of Mood States 2 (POMS 2) Short Form will be used for the quick assessment of affective states (Anger-Hostility; Confusion-Bewilderment; Depression-Dejection; Fatigue-Inertia; Tension-Anxiety; Vigour-Activity; Friendliness).
- The Fagerstrom Test of Nicotine Dependence (FTND) – A five item scale to index nicotine dependence.
- The Brief Psychiatric Rating Scale (BPRS) is a clinician rated assessment of current psychotic symptoms based on a short interview.
- The Psychotomimetic States Inventory (PSI) is a self-rated scale of transient psychotic symptoms.
- SF-12 is a short scale that measures social functioning.
- A semi-structured interview detailing the patient's alcohol and drug use history will also be used.
- The Alcohol TimeLine Follow Back (TLFB) is a drinking assessment method that obtains estimates of daily drinking and has been evaluated with clinical and nonclinical populations. Using a calendar, people provide retrospective estimates of their daily drinking over a specified time period. Several memory aids can be used to enhance recall (e.g., calendar; key dates serve as anchors for reporting drinking; standard drink conversion). The Alcohol TLFB has been shown to have good psychometric characteristics with a variety of drinker groups, and can generate variables that provide a wide range of information about an individual's drinking (e.g., pattern, variability, and magnitude of drinking).
- A drink diary will be given to each participant to take home in between Visits 8, 9 and 10. Participants will be asked to record their alcohol consumption every day in between study visits. Drink diaries are regularly used in alcohol research to record subjective alcohol consumption.
- Alcohol Craving Questionnaire - short-form (ACQ-NOW) is a 12-item scale that assesses current alcohol craving.

Validated Neurocognitive measures:

- Delay discounting (e.g. monetary choice questionnaire): this is a task that measures an individual's preference for immediate small award over a long term bigger gain.
- Prose recall task: this looks at episodic memory by testing participants recall of a short news broadcast.

- Stop signal task: Stop signal reaction time examines response inhibition, participants have to inhibit prepotent responses to stimuli on the screen when they see a cue or 'stop signal'.
- Working memory task (e.g. digit span WAIS-IV): Working memory measures an individual's ability to maintain and manipulate small amounts of information.
- Pattern recognition memory task (BPS-O Task) is a memory task that taps hippocampal functioning and requires participants to distinguish between perceptually similar items that they have seen before and those they have not.

Questionnaires that are not validated:

- The Pre-Screening questionnaire has been developed to assess suitability for inclusion into the trial.
- Adverse Effects Visual Analogue Scale (VAS) has been developed to measure adverse events during the ketamine infusion and treatment.
- Craving VAS: a one item visual analogue scale will be used to assess craving for alcohol anchored at one end with 'No desire to drink alcohol' and the other 'Very strong desire to drink alcohol'.

Breathalyser tests will be used at each visit for the following reasons:

- Screening & re-screening – To assess eligibility
- Baseline visit (1st infusion) – To assess eligibility/ensure safety of IMP administration/ensure patient is able to complete cognitive tasks and questionnaires, as well as engage with therapy/education
- Visit 3, 5, 7 & 8 – To ensure patient is able to complete cognitive tasks and questionnaires, as well as engage with therapy/education
- Visit 4 & 6 (2nd & 3rd infusion) – To ensure safety of IMP administration/ensure patient is able to complete cognitive tasks and questionnaires, as well as engage with therapy/education
- Visit 9 & 10 - To ensure patient is able to complete cognitive tasks and questionnaires

Once randomised, if a patient attends for any visit and does not blow 0 on the breathalyser the visit will be terminated (either for the primary purpose of safety on infusion visits or of data integrity on non-infusion visits) and the patient invited to re-attend to complete the visit within the allocated visit window.

Concomitant Medication: All prescription medication, over-the-counter medication, vitamins, and/or herbal supplements will be recorded on case report forms (CRFs).

Vital Signs: Resting pulse, pulse oximetry and blood pressure (BP) measurements will be measured at each visit phase for safety monitoring. Vital signs will be continuously monitored throughout the infusion until the participant has recovered. This monitoring will be recorded on a standard

observation chart, stored as source data. The eCRF will record 3 sets of readings, one prior to the infusion, another after the infusion terminates, and then finally after the participants recovery.

Physical Examination: Height, weight and oral/tympanic temperature will be recorded.

At screening a physician will perform a physical examination of the cardiovascular, respiratory, GI and neurological system to a level of detail that would be expected for a patient due to receive anaesthesia.

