### **9.12 Assessment of compliance**

Compliance includes both adherences to IMP and Protocol study procedures. The trial medication will be administered by the research anaesthetist only in the context of the patient attending the Clinical Research Facility. Patients will not be responsible for any trial medication. A member of the research team will ensure that the arrangements for each treatment visit are agreed with the participant and their carer. Where necessary, the researcher will assist in transportation. If a participant fails to attend a clinic visit for the infusion then the researcher will endeavour to contact the patient to identify the reason. Where possible an alternate appointment will be made within the infusion visit window (see Appendix B). If the participant fails to attend a clinic visit for the follow-up day the researcher will endeavour to contact the patient to identify the reason and where possible arrange an alternative visit within the follow up visit window (see Appendix B). All episodes of failure to attend will be recorded in the medical notes, CRF and protocol deviation log. If the participant misses 2 consecutive infusions, then they will be withdrawn from treatment and will be invited to attend follow up visits 9 and 10 as part of our intention to treat protocol. Noncompliance to the Protocol study procedures will be documented by the investigator and reported to the Sponsor as agreed. Persistent noncompliance (<80%) may lead the patient to be withdrawn from the study.

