Questionnaires and measurements scales to determine adverse effects/treatment adherence will be delivered in clinics by fully trained staff to ensure completeness. In cases where there are some missing data, the patient will be asked those questions on the telephone (a member of the Investigator Team will call him/her).

It will be the responsibility of the Lead Researcher to ensure the accuracy of all data entered into the CRF. The delegation log will identify all those personnel with responsibilities for data collection and handling, including those who have access to the trial database.

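### If a positive breath test ends visit 10, the plan gives no clear route to the drinking record behind both primary outcomes, and no not-at-random analysis covers the loss

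*Protocol*

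**What the plan says.** Protocol 7.9.1 applies the breath test at every visit, visits 9 and 10 included. Once a participant is randomised, "if a patient attends for any visit and does not blow 0 on the breathalyser the visit will be terminated", with "the patient invited to re-attend to complete the visit within the allocated visit window". Section 7.7 sets the window for visit "10 (23 to 25 weeks after visit 2", that is, days 161 to 175. No exception is made for TLFB.

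SAP 5.2 derives relapse and percentage days abstinent from TLFB. SAP 5.3 leaves the derivation to be confirmed. Appendix B schedules TLFB after randomisation at visits 4, 6, 8, 9 and 10.

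The primary analysis is complete case (protocol 13.3.2, SAP 6.5). Protocol 13.3.4 adds multiple imputation for relapse only, assuming missing at random (MAR). SAP 6.5 imputes both primary outcomes if more than 5% of participants have missing data. Neither document plans a not-at-random analysis. Section 7.11.1 says that 13.3.4 formally tests MAR.

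Relapse is described in two ways. Protocol 4.1 and SAP 5.2 require 5 drinks (men) or 4 drinks (women) on one occasion. Protocol 13.3.2 and the SAP's introductory text gloss it as resuming alcohol use.

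**The concern.** The rule can remove the outcome measurement because the participant has been drinking, in a trial whose outcome is drinking. If those who do not return at zero are more often relapsers, the analysed set understates relapse and overstates days abstinent. If this happens more in one drug group, the ketamine versus placebo comparison is biased, in either direction. Complete-case analysis does not correct loss that depends on unrecorded drinking, and neither does imputation under MAR. MAR cannot be tested from the observed data, and 13.3.4 contains no test, so the assurance in 7.11.1 is empty.

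The trial is exploratory and reports no p-values. Even so, protocol 13.2.1 wants an early indicator of whether a larger trial is warranted, and these estimates supply it.

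**Working it through.** **1. Provisions that might recover the TLFB**

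- Section 11.2, telephone: "In cases where there are some missing data, the patient will be asked those questions on the telephone". The paragraph opens with "Questionnaires and measurements scales to determine adverse effects/treatment adherence will be delivered in clinics" and names neither TLFB nor a terminated visit.
- Section 9.12, missed follow-up visit: staff will "where possible arrange an alternative visit within the follow up visit window", so it has the same time limit.
- Section 7.9.1, diary: "A drink diary will be given to each participant to take home in between Visits 8, 9 and 10". It is not a named source for either primary outcome.
- Sections 7.11 and 11.2 also promise every effort to continue assessments and to complete the data. These commitments are general and set no procedure.
- Earlier TLFBs could establish relapse for some participants, but SAP 5.3 does not say whether they count. They cannot supply days abstinent after visit 9. That visit falls at weeks 11 to 13 (days 77 to 91), leaving 84 to 98 of the 175 days in 13.3.2.

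**2. The plan's own precision**

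With 24 per drug arm and relapse of 50% against 25%: 0.25 ± 1.645 × √(0.50×0.50/24 + 0.25×0.75/24) = 0.028 to 0.472. This matches the 90% interval of 3% to 47% in protocol 13.2.1. As a relative risk, 6/24 against 12/24 is 0.50. The standard error of its log is √(1/6 − 1/24 + 1/12 − 1/24) = 0.408, so the 95% interval is 0.22 to 1.11.

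**3. Effect on relapse if earlier TLFBs are not used**

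Let r be true relapse and m the share of relapsers who lose the visit 10 TLFB; assume no non-relapser does. Observed relapse = r(1 − m)/(1 − rm). The documents give no value for m, so every value here is an assumption.

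- Equal loss, no true effect: both arms change alike and the RR stays 1.00.
- Equal loss, m = 10%, true 50% against 25%: 0.45/0.95 = 47.4% and 0.225/0.975 = 23.1%, so RR = 0.487 against a true 0.50. Relapse is understated in each arm.
- Unequal loss, no true effect, r = 50%, m = 10% placebo and 30% ketamine: 0.45/0.95 = 0.4737 and 0.35/0.85 = 0.4118, so RR = 0.87; reversed, 1.15.
- The same loss at r = 70%: 0.63/0.93 = 0.6774 and 0.49/0.79 = 0.6203, so RR = 0.92; reversed, 1.09.

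**4. Effect on relapse if earlier TLFBs are used**

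Protocol 2.1 gives about 50% relapsed at 3 months and 70% at 6. If visit 9 was completed, 0.50/0.70 = 71% of six-month relapsers are already recorded. Apply the 10% and 30% losses only to the later 0.20.

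- Simple counting: 0.68/0.98 = 0.6939 and 0.64/0.94 = 0.6809, so RR = 0.98; reversed, 1.02.
- MAR imputation given no relapse by month 3: 0.50 + 0.50 × 0.18/0.48 = 0.6875 and 0.50 + 0.50 × 0.14/0.44 = 0.6591, so RR = 0.96; reversed, 1.04.

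**5. Percentage days abstinent**

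Under the unequal loss at 50% relapse in step 3, the false difference is the gap between non-relapsers and relapsers × (0.4737 − 0.4118). Assumed gaps of 30, 50 and 70 points give 1.9, 3.1 and 4.3 points.

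**6. Why earlier relapses should be carried forward only in the imputation**

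Under 50% purely random loss after month 3, adding earlier relapsers to the complete cases gives (0.50 + 0.10)/(0.50 + 0.25) = 80%, against a true 70%. Imputation gives 0.50 + 0.50 × 0.10/0.25 = 70%.

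**The case against.** The route to loss is narrow. Participants have a two-week window and a telephone reminder. TLFB is retrospective ("people provide retrospective estimates of their daily drinking over a specified time period"), so any return at zero in the window recovers the record. If everyone returns, this rule causes no bias. The plan already allows for 50% drop-out, and nothing shows that the rule adds materially to it. Nor does anything in the documents support a threefold imbalance between arms blinded to drug. All of this stands, and it limits the size of the point.

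The telephone sentence in section 11.2 can be read more broadly, because that section also lists TLFB among its assessment tools. That is why the gap is the lack of a clear provision. A reader might infer that the protocol has no fallback at all, which goes further than the text allows.

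In step 4, imputation (0.96) lies further from 1.00 than counting (0.98). That is fair, and it shows that MAR imputation is not itself the cure. Counting fails worse under ordinary drop-out (step 6), and the delta adjustment is there for what remains.

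Omitting a not-at-random analysis from a proof-of-concept trial is not in itself an error. Here, however, a stated rule creates loss linked to the outcome, and 7.11.1 claims a safeguard that does not exist.

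**Conclusion.** The gap is real and worth closing, but its effect is probably small against an interval of 0.22 to 1.11. Equal loss barely moves the relative risk, although it understates relapse in each arm. Larger shifts (0.87 or 1.15) need both unequal loss and no use of earlier TLFBs; with earlier TLFBs used they shrink to about 0.96 to 1.04. Every loss rate is assumed, and the illustrations lose relapsers only.

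Two stronger readings are tempting. One is that the rule biases the trial towards ketamine: the documents give neither a frequency nor a direction. The other is that a positive reading is itself relapse, so that nothing is missing. The wording in 13.3.2 and the SAP introduction invites that, but protocol 4.1 and SAP 5.2 set a 5/4-drink threshold that a breath reading cannot establish. The conclusion rests on that threshold being the operative definition.

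**What to change.** 1. **Collection (7.9.1).** Keep the termination rule. State that after a terminated visit 10 the TLFB is still collected at a later sober contact, in person with a zero reading where possible and otherwise by telephone with the mode recorded. Set an outer time limit in advance. Exclude participants who have formally withdrawn, since 7.11.2 bars contact. Score everyone over one common period that the window can supply, or use each participant's observed days as denominator. Reconcile this with the 175 days in 13.3.2, because the window opens at day 161.
2. **Definition.** Reconcile the resumed-drinking gloss in 13.3.2 and the SAP introduction with the 5/4-drink definition. Under the latter, do not code a positive reading alone as relapse.
3. **Imputation (SAP 5.3, 6.5).** In the multiple-imputation analysis only, count a qualifying occasion on an earlier post-randomisation TLFB as observed relapse, and put earlier TLFB data in the imputation model.
4. **Sensitivity (7.11.1, 13.3.4, SAP 6.5).** Delete the claim that MAR is tested. Add a delta-adjusted not-at-random analysis for both primary outcomes, with the shift varied by drug group. Show missing counted as relapsed only as a labelled extreme, because 13.3.4 rejects it as an assumption.
5. **Reporting.** Give visit 10 terminations and later completions by arm.

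The cost is protocol and SAP wording, a call or later contact for those affected, and one more table. The downside is that a late or telephone TLFB may be less accurate, and sobriety cannot be verified by telephone.

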### 10.2 Recording adverse events

All adverse events will be recorded in the medical records and CRF only following consent.

If the investigator suspects that the subjects' disease has progressed faster due to the administration of the IMP, then he will record and report

this as an unexpected adverse event. Adverse events that are known to the IMP when used in its licensed indication (listed in Appendix C, or events that are disease related or related to procedures as listed in section 10.3.3) will only be recorded in the medical notes, however serious AEs will be recorded in the CRF and SAE log.

Clinically significant abnormalities in the results of objective tests (e.g. liver function, biochemistry) will also be recorded as adverse events. If the results are not expected as part of disease or IMP, these will also be recorded as unexpected. All adverse events will be recorded with clinical symptoms and accompanied with a simple, brief description of the event, including dates as appropriate. All adverse events will be recorded until 6 months post-treatment. All Serious Adverse Events will be reportable to the Sponsor from IMP administration up to 30 days post last IMP administration.

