### **11.2 Data collection tools and source document identification**

Data to be collected can be found in sections 7.5 and 7.7. Every effort will be made to maximise completeness of data. Trial data will be collected in an Electronic Case Report Form hosted on sealedenvelope.com, prepared using their “Red Pill” service ([www.sealedenvelope.com/redpill](http://www.sealedenvelope.com/redpill)). Source data documents will be defined at site prior to the start of the trial.

Full details of source data and documentation will be identified in a separate source document identification list but in summary will comprise of the following:

- Patient Clinical Record (medical notes)
- Trial specific source data worksheets and trial specific logs

- Laboratory test print outs
- Questionnaires and measurement scales
- Encrypted memory stick containing computer tasks data files and SCRAM-X data

Data to be recorded in the source data first and then transcribed into the CRF:

- Patient demographics; age, date of birth and initials
- Medical history including drug use, alcohol use, smoking
- Physical examination
- Patient eligibility assessment
- Allergies
- Concomitant medication
- Study IMP treatment
- Therapies: Psychoeducation Therapy, Relapse-prevention based CBT
- Clinical Assessment measurements: Vital signs, Blood and urine screen. On infusion visits (visits 2, 4 and 6) continuous monitoring of vital signs will occur through the infusion until the participant has recovered. This monitoring will be recorded on a standard observation chart and will be stored as source data. The eCRF will record 3 sets of readings, one prior to the infusion, another after the infusion terminates, and then finally after the participants recovery.
- Adverse Events (refer to section 10)
- Assessment tools:
  - Pattern Recognition Test
  - Stop Signal Reaction Time
  - Delay Discounting (monetary choice questionnaire)
  - Working Memory (digit span WAIS-IV)
  - Prose Recall
  - SCRAM-X checks
  - BPRS
  - PSI
  - Adverse events VAS
  - Craving VAS
  - Fagerstrom smoking
  - Timeline follow Back
  - Drink diary
  - Reasons for drinking questionnaire
  - Columbia Suicide Severity Rating Scale
  - BDI
  - HAM-D
  - POMS

- STAI
- SF-12
- ACQ-NOW

The following data to be collected in the source documents but will not be collected in the CRF:

- Adverse events that are expected for the IMP and which are not serious and listed in section 10

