4.5 Purpose of the analyses

The purposes of the analyses are as follows:

- (i) to provide baseline descriptive data by trial arm;
- (ii) to assess the feasibility of data collection;
- (iii) to assess loss to follow-up at 3 and 6 months;

- (iv) to assess the proportion of missing data at 6 months;
- (v) to provide descriptive outcome data by trial arm (ketamine vs placebo, psychotherapy vs psychoeducation, and all four arms individually) at 6 months;
- (vi) to provide relative risks (with 95% confidence intervals) for relapse of alcohol consumption comparing (a) ketamine vs placebo; (b) ketamine plus psychotherapy vs ketamine plus psychoeducation; (c) ketamine plus psychotherapy vs placebo plus psychoeducation;
- (vii) to provide mean difference (with 95% confidence intervals) for percentage of days abstinent at 6-month follow-up for the same combinations by arm as for (vi); and
- (viii) to descriptively report adverse events.

All inferential analyses are to be regarded as exploratory and viewed with caution due to lack of statistical power and multiple testing. For the primary outcomes, the primary analyses will be performed on an intention to treat (ITT) basis using complete case data only (see Section 6.5 for approaches to missing primary outcome data). As a sensitivity analysis, the inferential analyses for the primary outcomes only (vi and vii above) will be performed using only those participants deemed to have completed their allocated interventions to a specified degree (per protocol analysis). For the participants who receive ketamine, a per protocol treatment will be defined as receiving three or more infusions. No specification of a minimum treatment has been defined for psychotherapy/psychoeducation. Hence, all participants who receive placebo drug therapy will be considered as having been treated per protocol. For the secondary outcomes, only an ITT analysis using complete case data will be performed. All analyses will be performed by a statistician who is blinded to treatment allocation. All analyses will be performed using Stata v14.

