5.2 Endpoints

The primary and secondary outcome variables are set out in the Protocol, Final Version 12, 20.01.2020, Section 13.1 (reproduced in Table 2). There are two primary outcomes:

- 1) relapse (defined as 5 drinks (8.1 units alcohol) in men and 4 drinks (6.5 units alcohol) in women on a single occasion) at 6-month follow-up; binary outcome; and
- 2) percentage days abstinent (not using alcohol at all) at 6-month follow-up; percentage, to be analysed as a continuous variable.

The two primary outcomes are to be derived from timeline follow-back.

There are 19 secondary variables, derived from 16 secondary outcomes (Protocol, Final Version 12, 20.01.2020, Section 13.1.2; depression is measured by two variables, Beck Depression Inventory and Hamilton Depression Scale; Short Form Health Survey 12 (SF-12) produces a physical and a mental component scale; psychotic symptoms is measured by two variables, Brief Psychiatric Rating Scale and Psychotomimetic States Inventory).

- 1) maximum number of days of continuous abstinence within the first 3 months (time-line follow back); continuous;
- 2) percentage days abstinent at 3 months (time-line follow back); percentage, to be analysed as a continuous outcome;
- 3) Profile of Mood states; continuous;
- 4) Beck Depression Inventory; continuous;
- 5) Hamilton Depression Scale; continuous;
- 6) Speilberger Trait Anxiety Inventory; continuous;
- 7) Brief Psychiatric Rating Scale; continuous;
- 8) Psychotomimetic States Inventory; continuous;
- 9) Fagerstrom Test of Nicotine Dependence (FTND; smokers only); continuous;
- 10) Alcohol craving (visual analogue scale); continuous;
- 11) Alcohol Craving Questionnaire - short-form (ACQ-NOW);
- 12) Short Form Health Survey 12 (SF-12), physical component scale (PCS); continuous;
- 13) Short Form Health Survey 12 (SF-12), mental component scale (MCS); continuous;
- 14) episodic memory (Prose Recall); continuous;
- 15) delay discounting; continuous;
- 16) response inhibition (Stop Signal Reaction time); continuous;
- 17) working memory; continuous;
- 18) hippocampal functioning (Pattern Recognition Test); continuous; and
- 19) adverse effects (visual analogue scale); continuous.

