5.3 Derived variables

The only derived variables will be the binary relapse variable and the number/percentage of days abstinent, to be derived from timeline follow-back data. Further details are to be confirmed.

6 General analysis considerations

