6.6 Adverse events

Data on adverse events will be set out descriptively by trial arm.

7 Audit trail

Date of SAP	SAP version number	Date presented to Trial management group/Trial steering committee	Significant amendments since previous version	Date approved
15 June 2016	1.0	15 June 2016	N/A	15 June 2016
2 December 2019	1.1	5 December 2019	1. Inferential analyses to be adjusted by site (Section 7.3)	5 December 2019
27 January	1.1 (supersedes v1.1. 2/12/2019)	27 January 2020	1. Definition of primary outcome refined and data source for primary outcome confirmed (Section 5.2). 2. Protocol version amended in anticipation of submission (Version 12, 20.01.2020)	27 January 2020
11 March 2020	1.2	12 March 2020	1. Confirmation of use of Protocol Final Version 12, 20.01.2020 (throughout).	12 March 2020

8 References

1. *International Conference on Harmonisation of Technical Requirements for Registration of Pharmaceuticals for Human Use. Statistical Principles for Clinical Trials. Guideline E9.* http://www.ich.org/fileadmin/Public_Web_Site/ICH_Products/Guidelines/Efficacy/E9/Step4/E9_Guideline.pdf (last accessed 25 April 2016)

9 Appendix – example figures and tables

Figure 1 Participant flow diagram

[figure not shown]

Table 3 Participant characteristics at baseline

Participant characteristic	Ketamine + psychotherapy (N=)	Ketamine + psychoeducation (N=)	Placebo + psychotherapy (N=)	Placebo + psychoeducation (N=)
Gender; n (%)				
Male				
Female				
Age; mean (SD); [min, max]				

Table 4 Relapse of alcohol use and percentage of days abstinent at 6-month follow-up: intention to treat population using complete case data.

Outcome	Ketamine (n=)	Placebo (n=)	PT (n=)	PE (n=)	Ketamine + PT (n)	Ketamine + PE (n)	Placebo + PT (n)	Placebo + PE (n)	Ketamine vs placebo RR (95% CI)	Ketamine + PT vs Ketamine + PE RR (95% CI)	Ketamine + PT vs placebo +PE RR (95% CI)
Relapse; n (%) Timeline follow-back											
									Ketamine vs placebo mean difference (95% CI)	Ketamine + PT vs Ketamine + PE mean difference (95% CI)	Ketamine + PT vs placebo +PE mean difference (95% CI)
Percentage days abstinent; mean (SD); median [IQR] Timeline follow-back											

PE: Psychoeducation

PT: Psychotherapy

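### Three vital-sign sets per infusion go into the eCRF, but no analysis section summarises them, so the by-arm safety output would probably miss ketamine's common non-serious blood-pressure and heart-rate effects

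*Protocol*

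**What the plan says.** **Collection.** Vital signs are watched continuously during each infusion and charted as source data. For the database, protocol 7.9.1 states: "The eCRF will record 3 sets of readings, one prior to the infusion, another after the infusion terminates", and a third set follows once the participant has recovered. Sections 7.5, 7.7 and 11.2 say the same for visits 2, 4 and 6. Section 7.9.1 lists pulse, pulse oximetry and blood pressure, and gives safety monitoring as the purpose.

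**Adverse event recording.** Protocol 10.2 opens broadly: "All adverse events will be recorded in the medical records and CRF only following consent". It then makes an exception for effects already known for ketamine (Appendix C) and for disease-related or procedural events. These "will only be recorded in the medical notes, however serious AEs will be recorded in the CRF and SAE log". Section 11.2 lists, among data kept in source documents but not in the CRF: "Adverse events that are expected for the IMP and which are not serious and listed in section 10". Appendix C classes raised blood pressure and raised heart rate as common, and bradycardia, arrhythmia and hypotension as uncommon.

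**Analysis.** The only safety item among the eight purposes in SAP 4.5 is "to descriptively report adverse events". SAP 6.6 says: "Data on adverse events will be set out descriptively by trial arm". SAP 5.2 has two primary outcomes and then states: "There are 19 secondary variables, derived from 16 secondary outcomes". SAP 5.3 adds: "The only derived variables will be the binary relapse variable and the number/percentage of days abstinent". Protocol 13.3.3 plans attrition overall and by arm with a 95% confidence interval.

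**The concern.** Safety and tolerability is primary objective 2. Raised blood pressure and heart rate stand in the first row of the risk table in protocol 2.5. The dose of 0.8 mg/kg exceeds the 0.5 mg/kg that protocol 9.6 calls usual in depression and the 0.5 mg/kg that protocol 2.4 cites for previous work in recently detoxified patients. The haemodynamic response at this dose, in this population, is something a phase II safety objective should describe.

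The plan collects the data for that description and then does not use them. If the adverse event route is also closed to the common non-serious effects, the by-arm safety output would show serious cardiovascular events and little else on this known risk.

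**Working it through.** The plan states no figure on this point, so there is nothing to reproduce. The check follows the data from collection to output and then gauges the size.

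**1. Is there a planned output for the readings?**
- Protocol 13.1 to 13.3: no vital-sign outcome or summary.
- SAP 4.5: eight purposes, none of them vital signs.
- SAP 5.2 and Table 2: 2 + 19 = 21 outcome variables, of which 0 are vital signs.
- SAP 5.3: no change from the pre-infusion value.
- SAP Tables 3 to 8: no vital sign.
- Adverse effects VAS: self-reported, with examples such as nausea and anxiety (protocol 7.5), and analysed at 6 months (SAP Table 2). It cannot show blood pressure on infusion days.

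**2. Would adverse event counts carry the information?** Four pieces of text bear on this.
- The opening sentence of 10.2 points to CRF recording of all events.
- The rule that follows it is more specific. It names Appendix C and keeps non-serious events of that kind in the notes.
- Section 11.2 agrees in direction, but refers to events listed in section 10. The list in 10.3.3 does not name raised blood pressure or heart rate, although 10.2 brings in Appendix C by reference.
- A later sentence in 10.2 turns clinically important abnormal test results into adverse events. Its examples are laboratory tests, but they are only examples.

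Read with the specific rule prevailing, non-serious blood-pressure and heart-rate events stay out of the CRF. The statistician's data come from the eCRF (protocol 11.3), so events held only in the notes would not arrive. This is the more likely reading, not a certain one.

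**3. Would counts help even if they were recorded?** Assume that Appendix C's common band (1% to under 10%, anaesthetic use) applies per participant at this dose. Expected events of one type among 48 ketamine participants:
- 48 × 0.01 = 0.48
- 48 × 0.10 = 4.8

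That is about 0.5 to 4.8 participants, too few to describe the effect well.

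**4. How much do the readings hold?**
- Infusions if all are given: 96 × 3 = 288. eCRF sets: 288 × 3 = 864, or 432 per drug arm.
- At visit 2, randomisation and first infusion coincide, so up to 48 per drug arm contribute. The 95% confidence interval half-width for the difference in mean change is t(94) × √(2/48) × SD = 1.986 × 0.204 × SD = 0.405 SD.
- The documents give no SD. Assuming 10 to 15 mmHg for change in systolic pressure: 0.405 × 10 = 4.1 to 0.405 × 15 = 6.1 mmHg. Assuming 8 to 12 bpm for pulse: 0.405 × 8 = 3.2 to 0.405 × 12 = 4.9 bpm.
- Visits 4 and 6 would be less precise if infusions are missed.

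**5. What would the readings miss?** No clock time is set for the reading after the infusion ends. Protocol 2.2 gives a distribution-phase half-life of 10 to 15 minutes. On simple exponential decay, a 15-minute delay leaves 0.5^(15/15) = 50% to 0.5^(15/10) = 35% of the concentration, a fall of 50% to 65%. The recorded values may therefore understate the peak, which stands only on the source chart.

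**The case against.** The case for leaving the plan alone has substance.

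- **Vital signs are for monitoring, not an outcome.** Section 7.9.1 says so, and no promised report is broken. This stands. It makes the point an improvement, not a correction of an error.
- **Objective 2 already has measures.** The protocol summary ties tolerability to drop-out, attrition is reported by arm, adverse events are described by arm, and reasons for stopping treatment go into the CRF (7.11.1). This stands too, but none of these describes the size of a blood-pressure or heart-rate change.
- **SAP silence proves little.** The appendix tables are labelled examples, there is no adverse event shell although adverse events are planned, and 5.3 leaves details to be confirmed. It also cannot be exhaustive, since the SF-12 component scores in 5.2 are themselves derived. A vital-sign table is thus not forbidden. It is simply not planned.
- **The recording rule is not settled.** The opening and test-result sentences of 10.2 allow some CRF recording. Section 10.3.4 also defers collection of serious and non-serious events to a sponsor procedure that is not available here.

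Three stronger readings are tempting. A reader might infer that non-serious haemodynamic effects can reach no by-arm output at all; the mixed text supports only *probably*. A reader might infer that participants are under-monitored; monitoring is continuous, the charts are kept and serious events reach the CRF. A reader might take the post-infusion reading as near peak exposure; without a set time, the documents do not support that.

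**Conclusion.** The point holds as a cheap improvement. Three vital-sign sets per infusion, up to 864 in all, are entered in the eCRF with no planned summary. On the most specific reading of protocol 10.2, the by-arm safety output for primary objective 2 would probably miss ketamine's common non-serious effects on blood pressure and heart rate.

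The absence of a planned summary is firm and does not depend on how 10.2 is read: even if every event entered the CRF, the readings would still have no output. The loss through adverse event recording is likely but not certain. The half-width of 0.41 SD assumes 48 participants per drug arm at visit 2. The mmHg and bpm figures rest on assumed SDs, and the expected event counts on applying anaesthetic-use frequencies per participant. Nothing is lost for good, because the readings are kept and can be summarised.

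**What to change.** - In SAP 6.6, add one descriptive table, ketamine versus placebo by infusion visit (2, 4 and 6). Show blood pressure, pulse and oxygen saturation at the three eCRF time points, and the change from the pre-infusion value.
- In SAP 5.3, add that change as a derived variable.
- Produce the table only after the primary and secondary analyses are final. SAP 4.4 and 4.5 require a statistician blinded to allocation, and a clear difference in the readings could show which coded arm is ketamine.
- State under the table that the post-infusion reading has no set time, so the readings may miss the peak during infusion.

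The cost is a little analysis work and a blinding risk that the ordering controls. No new procedure for participants, data collection or protocol change is needed.
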